12.3 Record Retention

To enable evaluations and/or audits from regulatory authorities, the investigator agrees to keep records, including the identity of all participating subjects (sufficient information to link records), all original signed informed consent forms, serious adverse event forms, source documents, and detailed records of treatment disposition in accordance with EU GCP, local regulations, or as specified in the Clinical Study Agreement, whichever is longer. Data will be retained for a minimum of 25 years or for the time-period required to meet regulatory requirements defined for this trial.

13 Trial management

13.1 Trial steering committee (TSC)

A TSC will oversee the running of the trial and ensure that it is being conducted in accordance with the principles of GCP and the relevant regulations.

14 Study monitoring and auditing

Study monitoring visits will be conducted by NHS Greater Glasgow and Clyde (GG&C) Monitors. The level of monitoring will be based on the outcome of the completed monitoring risk assessment, and will be clearly documented in the monitoring plan which will be approved by the NHS GG&C Research Governance Manager / Academic Lead Clinical Trial Monitor. As standard, monitoring visit(s) will cover site file review, review of Informed Consent Forms (ICFs), Source Data Verification (SDV) and Serious Adverse Event (SAE) review as per monitoring plan objectives.

15 Ethical considerations

The study will be carried out in accordance with the World Medical Association Declaration of Helsinki (1964) and its revisions (Tokyo [1975], Venice [1983], Hong Kong [1989], South Africa [1996] Edinburgh [2000], Seoul [2008] and Fortaleza

[2013]). Favourable ethical opinion will be sought from the East of Scotland Research Ethics Committee (REC) before patients are entered into this clinical trial. Patients will only be allowed to enter the study once they have provided written informed consent. The CI will be responsible for updating the REC of any new information related to the study. The participant will remain free to withdraw from the study at any time without giving reasons and without prejudicing his/her further treatment.

16 Statement of indemnity

The trial is sponsored by NHS Greater Glasgow & Clyde and the University of Glasgow. The sponsor will be liable for negligent harm caused by the design of the trial. NHS indemnity is provided under the Clinical Negligence and Other Risks Indemnity Scheme (CNORIS). The NHS has a duty of care to patients treated, whether or not the patient is taking part in a clinical study, and the NHS remains liable for clinical negligence and other negligent harm to patients under its duty of care.

17 Funding

This trial is funded by the British Heart Foundation (PG/17/23/32850) and trial medications are supplied by the drug company Novartis who produce both valsartan (the standard treatment) sacubitril/valsartan (the experimental treatment).

18 Sponsor responsibilities

Appendix 1: Clinically notable laboratory values

Clinically notable laboratory abnormalities for selected tests based on a percent change from baseline:

Haematology

Hematocrit >50% increase, >20% decrease
Haemoglobin >50% increase, >20% decrease
Platelet count >75% increase, >50% decrease
RBC Count >50% increase, >20% decrease
WBC count >50% increase, >50% decrease

Biochemistry

Alkaline phosphatase >100% increase
ALT >150% increase
AST >150% increase
BUN >50% increase
Chloride >10% increase, >10% decrease
Creatinine >50% increase
Potassium >20% increase, >20% decrease
Total bilirubin >100% increase

Appendix 3: Patient global assessment questionnaire

CMR	Cardiovascular Magnetic Resonance imaging
CNP	C-type Natriuretic Peptide
COPD	Chronic Obstructive Pulmonary Disease
CRT	Cardiac Resynchronisation Therapy
DBP	Diastolic Blood Pressure
ECG	Electrocardiogram
ED	Emergency Department
FSH	Follicle-Stimulating Hormone
GDF-15	Growth Differentiation Factor-15
GP	General Practice
HF	Heart Failure
hsTnI	High Sensitive Troponin-I
ICD	Implantable Cardioverter-Defibrillator
LAVI	Left Atrial Volume Index
LVEF	Left Ventricular Ejection Fraction
LVESVI	Left ventricular End-Systolic Volume Index
LVSD	Left Ventricular Systolic Dysfunction
MedDRA	Medical Dictionary for Regulatory Activities
MI	Myocardial Infarction
MMP-9	Matrix Metallopeptidase 9
MR-proADM	Mid-Regional pro-Adrenomedullin
MR-proANP	Mid-Regional pro-Atrial Natriuretic Peptide
MRA	Mineralocorticoid Receptor Antagonist
MRI	Magnetic Resonance Imaging
NT-proBNP	N-terminal-pro hormone B-Type Natriuretic Peptide
NYHA	New York Heart Association
OTC	Over-the-Counter
PT	Preferred Term
QTc	QT interval corrected for heart rate
SAE	Serious Adverse Event
SAP	Statistical Analysis Plan
SBP	Systolic Blood Pressure
SD	Standard Deviation
SOC	System Organ Class

SST2	Somatostatin Receptor Subtype 2
SUSAR	Suspected Unexpected Serious Adverse Reaction
TIA	Transient ischemic attack
TIMP-1	Tissue Inhibitor Of Metalloproteinases 1

1. INTRODUCTION

1.1. STUDY BACKGROUND

Left ventricular systolic dysfunction (LVSD) and heart failure (HF) remain relatively common among survivors of myocardial infarction. This is because a large proportion of patients are not eligible for reperfusion therapy (i.e. those with non ST-segment elevation myocardial infarction) and many patients suffer recurrent episodes of infarction, leading to cumulative left ventricular damage over time.

In PARADIGM-HF, a combination of neprilysin inhibitor (sacubitril) and angiotensin receptor blocker (valsartan), reduced the risk of heart failure hospitalisation and death in patients with heart failure due to left ventricular systolic dysfunction or reduced ejection fraction (HF-REF), compared to an angiotensin-converting-enzyme inhibitor (ACEi) (enalapril).

The objective of RECOVER-LV is to obtain information on the cardiac effects of sacubitril/valsartan in patients with LVSD, compared to valsartan alone.

1.2. STUDY OBJECTIVES

1.2.1. PRIMARY OBJECTIVE

To investigate the potential benefit of sacubitril/valsartan vs. valsartan in attenuating adverse left ventricular remodelling in high risk asymptomatic patients post myocardial infarction as a result of residual left ventricular systolic dysfunction.

1.2.2. SECONDARY OBJECTIVES

To provide understanding of the cardiac effects and mechanisms of action of sacubitril/valsartan in patients with LVSD.

1.3. STUDY DESIGN

Randomised, double-blind, clinical trial.

1.4. RANDOMISATION

Section 12.1 of the study protocol states:

"Randomisation will be in a 1:1 ratio and stratified by LVESVI $\leq 45\text{ml}/\text{m}^2$ / $> 45\text{ml}/\text{m}^2$ as measured by baseline CMR, and whether or not the patient is being prescribed diuretics at baseline, with the randomisation schedule computer generated by the method of randomised permuted blocks, with random block lengths of 4 and 6."

1.5. SAMPLE SIZE AND POWER

Section 11.1 of the study protocol states:

"A sample size of 100 patients is proposed. This is based on the calculation that 45 patients per treatment group provides >90% power (α level = 0.05) to detect a difference of 6mL/m² in LVESVI (standard deviation = 7.8mL/m²) and accounting for a discontinuation rate of 10% (lost to follow up, development of heart failure or death). A 6mL/m² difference in LVESVI represents a minimally important difference."

Recruitment of 100 patients in 18 months requires a monthly recruitment rate of 5.6 patients/month or 1.4 patients/week.

1.6. STUDY POPULATION

Patients aged \geq 18 years with asymptomatic left ventricular systolic dysfunction (i.e. no evidence of clinical and/or radiological heart failure) >3 months post-acute myocardial infarction. A full list of inclusion and exclusion criteria is given in section 5.1 of the study protocol.

1.7. STATISTICAL ANALYSIS PLAN (SAP)

1.7.1. SAP OBJECTIVES

The objective of this SAP is to describe the final statistical analyses to be carried out for the randomised controlled trial of the RECOVER-LV study.

1.7.2. GENERAL PRINCIPLES

Data will be summarised for all participants and by randomised treatment group where appropriate. Categorical variables will be summarised with the number of observations and missing values, and number and percentage of participants falling into each category. Continuous variables will be summarised using the number of observations and number missing, mean, standard deviation (SD), median, 25th and 75th quartiles (Q1 and Q3 respectively), minimum and maximum values. Rates of recruitment and retention will be summarised as counts and percentages with 95% confidence intervals.

All efficacy outcomes will be analysed using regression analysis models that are adjusted for the baseline value of the outcome in question and whether or not taking diuretics at baseline. Efficacy outcomes will be summarised at baseline, 12 months and for the change from baseline at 12 months, presented overall and by treatment group. The model's intervention group treatment effect (and 95% CI) and p-value will be presented for outcome results measured at 12 months. All biomarker outcomes will additionally be summarised at 6 months and for the change from baseline at 6 months. Furthermore, a repeated measures linear regression model will be performed for each biomarker outcome, adjusting for the main effects of time-point and randomised group and the interaction between time-point and randomised group. The intervention group

treatment effect and time-point effect (and 95% CIs) will be presented with p-values for these main effects and their interaction.

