11.3 Statistical analysis

The study will have a comprehensive Statistical Analysis Plan, which will be authored by the Trial Statistician and agreed by the Investigators before the final unblinded analysis. Analysis will be done on an intention-to-treat basis. The Robertson Centre for Biostatistics, functional unit of the Glasgow Clinical Trials Unit, a fully registered UK CRN Clinical Trials Unit, will manage and analyse trial data.

The primary analysis will compare LVESVI at 12 months between randomised groups using a linear regression model, adjusted for baseline LVESVI, and whether or not taking diuretics at baseline. Similar methods will be applied to secondary outcomes. Safety data will be summarised without formal statistical comparison.

12 Data handling

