12.1 Randomisation

Randomisation will be in a 1:1 ratio and stratified by LVESVI ≤45mL/m² / >45mL/m² as measured by baseline CMR, and whether or not the patient is being prescribed diuretics at baseline, with the randomisation schedule computer generated by the method of randomised permuted blocks, with random block lengths of 4 and 6. The allocation for each patient will not be known to researchers until the point of randomisation. The full allocation sequence will be stored in a secure area of the Robertson Centre for Biostatistics network, with access restricted to those responsible for maintenance of the randomisation system. Study statisticians will not have access to the allocation schedule until the database has been locked, and all

analysis programs have been validated according to a prespecified statistical validation plan.

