2.4. EFFICACY OUTCOMES

2.4.1. PRIMARY OUTCOME

The change in indexed left ventricular end-systolic volume (LVESVI) from baseline to the 12 month follow-up visit will be summarised overall and by randomised group and compared between randomised groups using a linear regression model adjusted for baseline LVESVI, diuretic use at baseline and time from baseline to the 12 month follow-up visit.

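### Minor, free improvement: add the LVESVI randomisation stratum to the secondary and tertiary 12-month models, whose standard errors may otherwise be slightly too wide

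*SAP*

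**What the plan says.** SAP 1.4, repeating Protocol 12.1, states "Randomisation will be in a 1:1 ratio and stratified by LVESVI", cut at 45 mL/m², and by whether diuretics are prescribed at baseline. This makes four strata, "with the randomisation schedule computer generated by the method of randomised permuted blocks" of length 4 and 6.

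The primary model in SAP 2.4.1 is a "linear regression model adjusted for baseline LVESVI, diuretic use at baseline and time from baseline to the 12 month follow-up visit". It contains LVESVI because LVESVI is the outcome's own baseline there.

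For everything else, SAP 2.4.2 and 2.4.3 refer back to SAP 1.7.2 and add no covariate. That section has the models "adjusted for the baseline value of the outcome in question and whether or not taking diuretics at baseline". Protocol 11.3 says only: "Similar methods will be applied to secondary outcomes".

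For biomarkers, SAP 1.7.2 adds a repeated measures model, "adjusting for the main effects of time-point and randomised group and the interaction between time-point and randomised group". LVESVI is not named there either.

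**The concern.** Blocking within strata makes the arms nearly equal on the stratum. If the stratum predicts the outcome, the difference between arms varies less from trial to trial than under simple randomisation. A model without the stratum cannot see this. It leaves the stratum's share of variation in the residual and reports a standard error that still includes it. The interval is then wider than it need be and the test rejects less often than its nominal level.

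Here one of the two stratification factors enters every 12-month model and the other enters only the primary model. The documents give no reason for the difference. At stake is a little precision in the secondary and tertiary results, which could be had at almost no cost.

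**Working it through.** **Outcomes affected.** SAP 2.4.2 names 7: NT-proBNP, hsTnI, LVEDVI, LAVI, LVEF, LV mass index and the patient global assessment. SAP 2.4.3 names 6 remodelling biomarkers, 10 neurohormones and 4 further CMR measures, so 20. In total 7 + 20 = 27, not counting the unnamed other biomarkers.

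**The plan's own figure.** Protocol 11.1 gives 45 per group, a difference of 6 mL/m², SD 7.8 and alpha 0.05 (taken as two-sided). The SE is 7.8 × √(2/45) = 1.644, and 6/1.644 = 3.65. Power is Φ(3.65 − 1.96) = 95.4%, or 95.0% with the noncentral t, which meets the stated >90%. After 10% loss, 45/0.9 = 50 per group, or 100 in all. The figure reproduces, and this point does not touch it.

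**Formula for the omission.** Let R² be the share of outcome variance that the stratum explains beyond own baseline and diuretic use. The model without the stratum reports an SE larger by a factor of about 1/√(1 − R²). For R² of 2%, 5% and 10% this is 1.010, 1.026 and 1.054.

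**Simulation.** From the documents: 100 patients, blocks of 4 and 6 within the four strata, 10% loss (90 analysed), own baseline and diuretic use in every model. Assumed: 50% above 45 mL/m², 30% on diuretics, a continuous outcome with residual SD 1, about 240,000 replicates per setting. As a check on scale, √(2/45) = 0.2108, close to the simulated 0.2118.

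| Assumed partial R² | 0% | 2% | 5% | 10% |
|---|---|---|---|---|
| Mean reported SE, stratum omitted | 0.2118 | 0.2118 | 0.2118 | 0.2119 |
| Mean reported SE, stratum included | 0.2120 | 0.2098 | 0.2066 | 0.2011 |
| Empirical SD of estimate, omitted | 0.2128 | 0.2107 | 0.2072 | 0.2032 |
| Empirical SD of estimate, included | 0.2129 | 0.2106 | 0.2065 | 0.2018 |
| Size of 5% test, omitted | 5.0% | 4.8% | 4.5% | 4.0% |
| Size of 5% test, included | 5.0% | 5.0% | 4.9% | 5.0% |
| Power at 0.59 SD, omitted | 78.5% | 78.8% | 79.0% | 79.4% |
| Power at 0.59 SD, included | 78.4% | 79.3% | 80.4% | 82.5% |

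Two comparisons must be kept apart.

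- *Model against model*: 0.2118/0.2098, 0.2118/0.2066 and 0.2119/0.2011 give 1.0%, 2.5% and 5.4%.
- *Reported SE against the true spread of the same estimate*: 0.2118/0.2107, 0.2118/0.2072 and 0.2119/0.2032 give 0.5%, 2.2% and 4.3%. This is the proper measure of an SE that is too wide.

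The true spread itself hardly changes: at 10%, 0.2032/0.2018 is a difference of 0.7%. What is off is mainly the reported SE. Adding the stratum changes power by −0.1, +0.5, +1.4 and +3.1 points.

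**Sensitivity.**

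- A smaller simulation (8,000 runs, 30% at or below 45 mL/m²) gave sizes of 4.8%, 4.3% and 3.7% at 2%, 5% and 10%, with a Monte Carlo error of about 0.2 points. The reported SE exceeded the true spread by about 1%, 2% and 5%. A further run at 5% gave a size of 4.8%.
- With 80% of patients above the cut, sizes at 5% and 10% are 4.6% and 4.1%. With 90% above, they are 4.7% and 4.2%.
- If LVESVI acts continuously (normal), the stratum carries φ(c)²/[p(1 − p)] of its explained variance: 64%, 49% or 34% at a 50/50, 80/20 or 90/10 split. Size then stays between 4.4% and 4.9% throughout.

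**The case against.** The strongest reply is that nothing here is wrong. The Protocol asks for similar methods, and the SAP supplies them by putting each outcome's own baseline in place of LVESVI. The partial R² is unknown and may be zero. For LVEDVI and LVEF the outcome's own baseline probably carries most of what LVESVI would add. The only consequence is caution. All of this stands, and it is why the point is an optional improvement. It is less evident that own baseline does the same work for circulating biomarkers.

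A reader might infer that the Protocol and SAP contradict each other. They do not. A reader might also take 5.4% as the error in the reported SE. That figure compares two models; against the true spread the excess is 4–5%, and only at the top of the assumed range.

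A stronger reading of the repeated measures sentence is tempting: that it also omits own baseline and diuretic use, with a larger loss. The text does not establish this. The same section opens with "All efficacy outcomes will be analysed using regression analysis models that are adjusted for the baseline value of the outcome in question" and diuretic use, and that rule can supply both terms. Any figure for that model's group main effect would also depend on factor coding and on whether baseline is a time-point, and the SAP gives neither. None is offered here.

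The primary model also contains time to the 12-month visit, which SAP 1.7.2 lacks. That is not a stratification factor and lies outside this point.

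**Conclusion.** The point holds as a minor, free improvement. SAP 1.7.2 leaves one of the two randomisation factors out of the 12-month models for 27 named outcomes. To the extent that the LVESVI stratum is prognostic beyond own baseline and diuretic use, their intervals are slightly too wide and their tests slightly conservative. For assumed partial R² of 0% to 10%, the excess over the true spread runs from nothing to about 4–5%, and test size from about 5.0% down to about 4.0%. The effect is smaller if LVESVI acts continuously, and probably smallest for LVEDVI and LVEF.

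It would be wrong to conclude that type I error is inflated; it is not in any setting examined. The primary analysis already carries LVESVI, and the sample size is unaffected. The result rests on the assumed R², split and diuretic share. It also rests on a continuous outcome, so the figures may not apply to the patient global assessment, whose scale cannot be seen.

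**What to change.** In SAP 1.7.2, add the LVESVI stratum, or continuous baseline LVESVI as in the primary model, to every secondary and tertiary 12-month model. It should stand beside diuretic use and the outcome's own baseline where one exists; Protocol Table 9-1 schedules the patient global assessment only at weeks 26 and 52. Carry the same term into the biomarker repeated measures model.

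As a side note, state that model's other covariates and whether baseline is one of its time-points.

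The cost is one sentence and one degree of freedom out of about 90. Both stratification factors are needed to randomise, so they should be known for every patient. If the stratum turns out to predict nothing, about 0.1 point of power is lost.

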1.7.3. CURRENT PROTOCOL

The current protocol at the time of writing is version 7.0, dated 24/08/2020. Future amendments to the protocol will be reviewed for their impact on this SAP, which will be updated only if necessary. If no changes are required to this SAP following future amendments to the study protocol, this will be documented as part of the Robertson Centre Change Impact Assessment processes.

1.8. SOFTWARE

All statistical analyses will be carried out using R v4.0.0 [R Development Core Team 2020] or higher versions of this program. The final report will be provided as a password protected PDF document. Listings will be provided as excel files.

2. ANALYSIS

With the exception of analysis detailed in Subsection 2.4.3 Tertiary (exploratory) outcomes below, all analysis described in Section 2, in addition to the tertiary outcome change in ANP, will be produced in the first wave of outputs. The second wave of outputs will include the analysis of the remaining tertiary outcomes outlined.

2.1. STUDY POPULATION

The analysis population will comprise of all subjects randomised into the study.

2.2. SUBJECT DISPOSITION

The number and percentage of participants consenting to take part in the study will be summarised and randomised subjects will be summarised, overall and by randomised treatment group. The cumulative numbers of participants randomised to each treatment group will be reported in tabular form and graphically. The number and percentage of randomised subjects attending each study visit will also be presented with those that did not attend classified as either: Lost to follow-up, died, or did not attend. Reasons for ineligibility for study participation will be summarised for the consenting non-randomised subjects. The number and percentage of subjects withdrawing from the study medication and from study follow-up will be presented alongside the main reasons for withdrawal.

2.3. BASELINE CHARACTERISTICS

The following baseline characteristics will be summarised for all randomised subjects and by randomised intervention group, without formal statistical comparison:

- Cardiac MRI: height (m), weight (kg), BMI (kg/m²), body surface area (kg/m²), gadolinium contrast administered
- Physical Exam: NYHA class, third heart sound, pulmonary crepitations (area and location), pleural effusion (location), peripheral oedema (location), any other relevant abnormalities
- Medication history: loop diuretic, thiazide diuretic, ACE inhibitor, angiotensin receptor blocker, beta-blocker (except sotalol), mineralocorticoid receptor antagonist (MRA), statin, anti-platelet, anti-coagulant, nitrate, calcium channel blocker (CCB), alpha blocker, antiarrhythmic
- Vital signs: SBP (mmHg), DBP (mmHg), heart rate (bpm)
- Electrocardiogram results: heart rate (bpm), heart rhythm, PR interval (ms), QRS duration (ms), bundle branch block, QTc interval (ms), ST segment deviation, T wave inversion, Q wave inversion
- Spot urine collection
- Venepuncture: urea, creatinine, potassium, eGFR, haemoglobin, bilirubin, ALT, AST, ALP, hs-troponin I (hsTnI), HbA1c, NTproBNP
- Pregnancy: woman of child-bearing potential, FSH level, pregnancy test done, pregnancy test result
- Symptom Review: heart failure since last review, paroxysmal nocturnal dyspnoea, orthopnoea, dyspnoea at rest, dyspnoea on effort, fatigue, peripheral oedema, emergency admission to hospital, ED visit, urgent clinical visit, GP or other primary care consultation, intervention or treatment change (started or increased dose for all except ICD/CRT)
- Previous Medical History: time since index MI, known coronary artery disease, angina, MI, treatment for MI, CABG/PCI prior to MI, history of hypertension, paroxysmal AF, stroke, TIA, carotid artery disease, peripheral arterial disease, lower limb revascularisation, valve replacement, dizziness / hypotension / falls etc., COPD, asthma, cancer, diabetes, hypothyroidism and hyperthyroidism, smoking (status and pack year), alcohol consumption (intake level, average number of units per week), any other significant medical history

